9.6.1.3 Absolute Change in BMI from Baseline

BMI will be calculated as:

$$\text{BMI} = \text{Weight (kg)} / (\text{height (m)}^2)$$

9.6.1.4 Absolute Change in CFQ-R Respiratory Domain from Baseline

The CFQ-R is a validated CF-specific instrument that measures quality-of-life domains. Three different versions of CFQ-R forms have been used in the VX-661 program:

- CFQ-R for Children Ages 12 and 13 has a total of 35 questions to form 8 domains. All questions are scored 1, 2, 3, or 4.
- CFQ-R for Adolescents and Adult (subjects 14 years and older) has a total of 50 questions to form 12 domains. Question 43, which is scored 1, 2, 3, 4, or 5, is not used in calculating any domain; all the other 49 questions are scored 1, 2, 3, or 4.
- CFQ-R for Parents/Caregivers (subjects 13 years and younger) has a total of 44 questions to form 11 domains. Question 37, which is scored 1, 2, 3, 4, or 5, is not used in calculating any domains; all the other 43 questions are scored 1, 2, 3, or 4.

For all three CFQ-R versions, to calculate the score for each domain, the response scores on the negatively phrased questions are reversed (reversed scores = 5 – response scores) so that 1 always represents the worst condition and 4 always represents the best condition.

The scaled score for each domain ranges from 0 (worst condition) to 100 (best condition). It is calculated as follows:

$$\text{Scaled score for a domain} = 100 \times (\text{mean(scores of all questions in that domain)} - 1) / 3$$

The scaled score for a specific domain will not be calculated if more than half of the questions in the domain have missing scores. [REDACTED]

Scaled scores will be used in the efficacy analysis.

9.6.1.5 Time to First Pulmonary Exacerbation on TEZ/IVA

The time to first PEx is defined as the number of days from the first dose of TEZ/IVA to the first PEx event during the PEx Analysis Period.

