7.2 Pulmonary Exacerbation Analysis Sets

106/110 PEx Analysis Set and **108/110 PEx Analysis Set** are defined in **Error! Reference source not found.**. They include the subjects who received TEZ/IVA in parent study or Part A.

Analysis Population Name	Treatment Group	Description
106/110 PE Analysis Set	TEZ/IVA	Subjects randomized to TEZ/IVA in Study 106 and received treatment
	PBO-TEZ/IVA	Subjects randomized to placebo in Study 106 and who received TEZ/IVA in Study 110
108/110 PE Analysis Set	TEZ/IVA	Subjects randomized to IVA-TEZ/IVA sequence or PBO-TEZ/IVA sequence in Study 108 and who received treatment in Period 2 of Study 108
	IVA-TEZ/IVA	Subjects randomized to TEZ/IVA-IVA sequence or PBO-IVA sequence in Study 108 and who received treatment in Period 2 of Study 108 and who received TEZ/IVA in Study 110. Subjects in TEZ/IVA-IVA sequence who did not enroll in Study 110 treatment cohort will also be included in this group if they received treatment in Period 1.
	PBO-TEZ/IVA	Subjects randomized to TEZ/IVA-PBO sequence or IVA-PBO sequence in Study 108 and who received treatment in Period 2 of Study 108 and who received TEZ/IVA in Study 110. Subjects in TEZ/IVA-PBO sequence who did not enroll in Study 110 treatment cohort will also be included in this group if they received treatment in Period 1.

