8.2 Pulmonary Exacerbation Analysis Period

PEx Efficacy Analysis Period is defined as the time period from the first dose of TEZ/IVA in parent study (after the washout period, if applicable) or Study 110 Part A to the date of last efficacy assessment in parent study or Study 110 Part A, as highlighted in grey in [Table 8-1](#). Note for parent Study 108, only Period 2 is pooled.

Similarly, for subjects who participate in another qualified Vertex study before completing Study 110 assessments and re-enroll in Study 110, the PEx Efficacy Analysis Period will exclude the time between the last dose before the discontinuation from Study 110 and the first dose after re-enrollment in Study 110.

Table 8-1 PEx Analysis Period for PEx Analysis Sets			
Analysis Set	Analysis Period		
	Parent Study		Study 110 Part A
106/110 PEx Analysis Set	TEZ/IVA		TEZ/IVA
	PBO		TEZ/IVA
108/110 PEx Analysis Set	Period 1: TEZ/IVA	Period 2: IVA	TEZ/IVA
	Period 1: IVA	Period 2: TEZ/IVA	TEZ/IVA
	Period 1: TEZ/IVA	Period 2: PBO	TEZ/IVA
	Period 1: PBO	Period 2: TEZ/IVA	TEZ/IVA

	Period 1: IVA	Period 2: PBO	TEZ/IVA
	Period 1: PBO	Period 2: IVA	TEZ/IVA

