9.6.2.3.2 Subjects in 108/110 PEx Analysis Set

The analysis of time-to-first PEx for 108/110 PEx Analysis Set will be similar to that for 106/110 PEx Analysis Set.

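### SAP 9.6.1.5 does not tie the start of the time-to-first-exacerbation clock to the PEx Analysis Period; programmed as written, it gives some Study 108 rollovers event-free lead time

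*SAP*

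**What the plan says.** - **Clock.** SAP 9.6.1.5 counts the "number of days from the first dose of TEZ/IVA to the first PEx event during the PEx Analysis Period". It does not say which first dose is meant when a subject took TEZ/IVA in more than one period. Protocol 12.3.4.2 also starts at the first dose of the combination, without qualification.
- **Event window.** SAP 8.2 opens the PEx Analysis Period "from the first dose of TEZ/IVA in parent study (after the washout period, if applicable) or Study 110 Part A", and adds: "Note for parent Study 108, only Period 2 is pooled".
- **Groups.** SAP 7.2 places in the IVA-TEZ/IVA group "Subjects randomized to TEZ/IVA-IVA sequence or PBO-IVA sequence in Study 108 and who received treatment in Period 2 of Study 108", if they went on to TEZ/IVA in Study 110. The PBO-TEZ/IVA group is built in the same way: "Subjects randomized to TEZ/IVA-PBO sequence or IVA-PBO sequence in Study 108 and who received treatment in Period 2 of Study 108". Each group therefore joins one sequence that had TEZ/IVA in Period 1 with one that did not.
- **Non-rollovers.** On the strength of Period 1 treatment alone, SAP 7.2 also admits some who did not roll over: "Subjects in TEZ/IVA-IVA sequence who did not enroll in Study 110 treatment cohort will also be included in this group if they received treatment in" (the sentence ends by naming that period). The same rule applies to the TEZ/IVA-PBO sequence.
- **Analysis.** SAP 9.6.2.3.1 uses Kaplan-Meier curves by treatment group and censors event-free subjects at the end of the PEx Analysis Period. For Study 108, SAP 9.6.2.3.2 says: "The analysis of time-to-first PEx for 108/110 PEx Analysis Set will be similar to that for 106/110 PEx Analysis Set".

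**The concern.** In the two sequences with TEZ/IVA in Period 1, the first dose of TEZ/IVA and the opening of the event window are different dates. Period 1, the washout and Period 2 lie between them. A clock that starts at the earlier date, with events accepted only from the later one, makes all of that time event-free by construction. Event times and censoring times are both lengthened, and the SAP gives no delayed-entry rule to correct for it.

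The PBO-IVA and IVA-PBO subjects in the same two groups first receive TEZ/IVA in Study 110, so their clock starts there. Each curve would then combine two time origins, one of them with a guaranteed event-free lead. Both curves would look better than the data warrant, and better relative to the 108/110 TEZ/IVA group, whose first TEZ/IVA dose is in Period 2 and which has no such lead. Time to first PEx is a listed secondary endpoint, and Study 108 is one of the two parent studies on which SAP 7.1 focuses the efficacy analysis.

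**Working it through.** The plan states no event rate, survival figure or sample size for this endpoint, so there is no figure of its own to reproduce. The check has two parts: which dates the text gives, and how large the effect of the literal dates could be.

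**Dates by sequence (SAP Table 8-1, 7.2, 8.2 and 9.6.1.5)**

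| Period 1 / Period 2 | Group | First TEZ/IVA dose | PEx window opens (8.2) |
|---|---|---|---|
| IVA / TEZ/IVA; PBO / TEZ/IVA | TEZ/IVA | Period 2 | Period 2 |
| PBO / IVA | IVA-TEZ/IVA | Study 110 | Study 110 |
| TEZ/IVA / IVA | IVA-TEZ/IVA | Period 1 | Study 110 |
| IVA / PBO | PBO-TEZ/IVA | Study 110 | Study 110 |
| TEZ/IVA / PBO | PBO-TEZ/IVA | Period 1 | Study 110 |

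The two dates differ in two of the six sequences. SAP 6.2 gives 227 rollovers from Study 108 but no split by sequence. If the sequences were equal, 227 × 2/6 = 75.7, about 76 rollovers, or half of each affected group before the non-rollovers of SAP 7.2 are added.

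**Inputs for the illustration.** None of these is in the documents:
- constant first-PEx hazard h of 0.3 to 0.8 per year;
- lead L (Period 1 + washout + Period 2) of 16 to 32 weeks;
- half of each affected group with TEZ/IVA in Period 1.

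**Reading A: clock starts at the 8.2 date.** S(t) = exp(−h·t/52). There is no lead, so the bias is 0.

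**Reading B: clock starts in Period 1, events count only from Study 110.** For an affected subject, S(t) = exp(−h·(t − L)/52). The group curve is the average of A and B, so the overstatement is (B − A)/2.

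Central case, h = 0.5, L = 24, t = 48:
- A = exp(−0.5 × 48/52) = 0.630
- B = exp(−0.5 × 24/52) = 0.794
- group curve = (0.630 + 0.794)/2 = 0.712, or +8.2 points

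Ends of the range at Week 48:
- h = 0.3, L = 16: A = 0.758, B = 0.831, overstatement 3.7 points
- h = 0.8, L = 32: A = 0.478, B = 0.782, overstatement 15.2 points

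At Week 96 the same inputs give 2.8 points (h = 0.3, L = 16) to 7.3 points (h = 0.8, L = 32).

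**Reading C: Period 1 TEZ/IVA time counts, washout and Period 2 do not.** The event-free gap G is shorter than L; take G = 2L/3 (assumed). For t beyond the gap, S(t) = exp(−h·(t − G)/52). In the central case G = 16, S(48) = exp(−0.5 × 32/52) = 0.735 and the group curve is 0.683, or +5.2 points. The same ranges of h and L give 2.4 to 9.3 points at Week 48.

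**The case against.** The strongest reply is that the SAP already supplies the origin. Section 8.2 opens the PEx Analysis Period at a first dose of TEZ/IVA, after washout where applicable and with only Period 2 of Study 108 pooled. Section 9.6.1.5 uses the same phrase for the dose and names the same period, and 9.6.2.3.1 analyses the endpoint during that period. Read together, the dose for these rollovers is the first one in Study 110 and there is no lead. Protocol 12.3.1 also anchors Study 108 subjects at Period 2 rather than Period 1. The rate analysis already runs on the duration of the PEx Analysis Period, because SAP 9.6.2.2.1 uses its logarithm as the offset.

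Much of this stands. A careful programmer may well choose the 8.2 date, and the negative binomial offset needs no change. A reader might infer from 9.6.1.5 that exacerbation-free survival will certainly be overstated. The documents do not support that, because the zero-bias reading is open and reasonable.

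But no text makes that reading the rule:
- Section 8.2 defines the window, and 9.6.1.5 applies the window only to the event.
- Protocol 12.3.1 sets its anchor for the Efficacy Analysis and treatment-emergent periods, and that anchor includes ivacaftor monotherapy. For TEZ/IVA-IVA subjects it would give a third date, the first Period 2 ivacaftor dose.
- SAP 7.2 admits non-rollovers from these same sequences because of Period 1 treatment. Their only TEZ/IVA exposure is in Period 1, so pooling Period 2 alone leaves them no PEx Analysis Period. This gives a programmer some ground for treating Period 1 as qualifying exposure.

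Table 8-1 marks the included cells by grey shading, which is not visible in the text available for this review. It may settle whether Period 1 cells count for some subjects. If they do, not all of the lead is event-free, and Reading C applies in place of Reading B.

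**Conclusion.** The concern holds as an unanchored time origin with a conditional bias. Followed literally, SAP 9.6.1.5 and 8.2 together give TEZ/IVA-IVA and TEZ/IVA-PBO rollovers a clock that starts in Period 1 and an event window that opens in Study 110. On the assumed inputs, Week 48 PEx-free survival in the IVA-TEZ/IVA and PBO-TEZ/IVA groups would then read about 4 to 15 points too high. With the 8.2 date as origin the error is zero. If Period 1 TEZ/IVA time is meant to count, washout and Period 2 remain an event-free gap, with a smaller error.

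These sizes are illustrations. The hazard, the Study 108 period and washout lengths and the sequence split are not in the documents, and the non-rollovers added by SAP 7.2 would change the one-half share. The reach is limited to two of the three 108/110 groups, in a descriptive Kaplan-Meier analysis of a secondary endpoint; SAP 9.6.2 rules out between-group testing. The 106/110 set, the 108/110 TEZ/IVA group and the offset in the event-rate model are not affected by this choice of origin. The point is still worth correcting before programming, because a stated rule produces the error when it is followed to the letter.

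**What to change.** 1. In SAP 9.6.1.5, define time zero as the first TEZ/IVA dose within the subject's PEx Analysis Period under 8.2: the first dose in Study 106, in Study 108 Period 2 or in Study 110, whichever opens the period. This start date already determines the duration used for the negative binomial offset.
2. Reconcile SAP 7.2 with the Period 2 restriction in 8.2 by stating whether Period 1 TEZ/IVA time counts, for rollovers and for non-rollovers. If it counts, exclude washout and Period 2 time from the clock. If it does not, state how the non-rollovers admitted on Period 1 treatment can contribute.

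The cost is one sentence in 9.6.1.5, one clarification shared by 7.2 and 8.2, and one derivation line in the programming. No new data are needed.

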9.6.2 Analysis of Efficacy Endpoints

Most continuous endpoints during 110 Efficacy Analysis Period will be analyzed for subjects in 106/110 ES and 108/110 ES using a mixed-effects model for repeated measures (MMRM) with similar specification as in the parent study SAP/CSR, if applicable. However, these MMRM analysis will be restricted to the last visit at which the total number of subjects is approximately 70% of subjects from the respective parent study.

These continuous endpoints during 110 Efficacy Analysis Period will also be descriptively summarized for subjects in FAS who roll over from Study 103 and 111, where the patients carry *F/F* mutation.

No hypothesis testing will be done for between-group comparisons.

9.6.2.1 Absolute Change in Percent Predicted FEV₁ from Baseline

9.6.2.1.1 Subjects in 106/110 ES

The MMRM for 106/110 ES during 110 Efficacy Analysis Period will have the absolute change in ppFEV₁ from baseline (including all measurements up to Week 96 [inclusive], both on-treatment measurements and measurements after treatment discontinuation) as the dependent variable and the following fixed effects: treatment (PBO-TEZ/IVA, TEZ/IVA), visit, and treatment-by-visit interaction, sex and age group at screening (<18, ≥18 years old), parent study baseline ppFEV₁, and parent study baseline ppFEV₁-by-visit interaction.

The repeated-measures analysis will be based on the restricted maximum likelihood (REML) method assuming an unstructured (UN) covariance structure to model the within-subject errors. The denominator degrees of freedom will be based on the method proposed by Kenward-Roger. If the model fails to converge due to the UN covariance assumption, a compound symmetry (CS) covariance structure will be used to model the within-subject errors. In the MMRM approach, assuming that the data are missing at random, no imputation of missing data will be performed.

The number of subjects, least-squares (LS) means at scheduled visits within each treatment group along with the corresponding standard error (SE) and 95% confidence interval (CI) will be presented.

The LS means (±95% CI) for absolute change from baseline at each visit will also be plotted by treatment group.

In addition, the descriptive statistics for observed values and absolute changes from baseline in ppFEV₁ by treatment group will be presented at scheduled visits during 110 Efficacy Analysis Period.

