12.3.4.2 Analysis of Secondary [REDACTED] Efficacy Variables (Treatment Cohort)

- **Absolute change from baseline in ppFEV₁**

One of the secondary efficacy endpoints is the absolute change from baseline in ppFEV₁. The primary analysis for this secondary endpoint will be based on a mixed-effect repeated-measure model (MMRM), as applicable. The model will include the absolute change from baseline in ppFEV₁ as the dependent variable; treatment group, visit, and treatment-by-visit interaction as fixed effects; and subject as a random effect with or without adjustment for sex, age, baseline ppFEV₁.

In the model, visit will be treated as a class variable, assuming an unstructured covariance matrix to model the within-subject variability. This model imposes no assumptions on the correlational structure and is considered robust. Denominator degrees of freedom for the F test for fixed effects will be estimated using the Kenward-Roger approximation. If there is a convergence problem due to the use of an unstructured covariance matrix, a compound symmetry covariance structure will be used to model the within-subject errors. With a mixed-effects model based on a restricted maximum likelihood estimation used for the primary analysis and assuming that, conditional on fixed and random effects, data are missing at random, no imputation of missing data will be performed.

Descriptive summary statistics including number of subjects, mean, standard error, and least square mean (LS mean), along with the associated 95% CI will be provided for each visit.

- **Relative change from baseline in ppFEV₁**

Analysis of this variable will be performed using the same MMRM model as described for the absolute change from baseline in ppFEV₁.

- **Number of pulmonary exacerbations**

The number of pulmonary exacerbations will be analyzed using a negative binomial regression model as applicable. The independent variables will include visit, sex, age, baseline ppFEV₁. The event rate and 95% CI will be reported.

- **Absolute change from baseline in body mass index (BMI)**

Analysis of this variable will be similar to the model as described for the absolute change in ppFEV₁ from baseline, with the addition of baseline BMI as the covariate.

- **Absolute change from baseline in BMI z-score**

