9.6.2.4 Other Efficacy Endpoints

For all the other efficacy endpoints (including relative change in ppFEV₁ from baseline, absolute change in BMI from baseline, absolute change in BMI z- score from baseline, absolute change in CFQ-R Respiratory Domain Score from baseline, absolute change in weight from baseline, absolute change in weight z-score from baseline, absolute change in height z-score from baseline), the analysis will be similar to the analysis of absolute change in ppFEV₁ from baseline. Note that for CFQ-R Respiratory Domain Score, the Pooled 'Children Ages 12 and 13' Version and 'Adolescents and Adults' Version is used for MMRM based approach and descriptive summary, 'Parents/Caregivers' Version is also used for descriptive summary.

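### The only fallback for a non-converging unstructured MMRM is compound symmetry, so late-visit confidence intervals and LS means could be wrong in either direction

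*SAP*

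**What the plan says.** For ppFEV₁ in the 106/110 Efficacy Set, SAP section 9.6.2.1.1 models the change from baseline, "including all measurements up to Week 96 [inclusive], both on-treatment measurements and measurements after treatment discontinuation", by REML, "assuming an unstructured (UN) covariance structure to model the within-subject errors". It adds: "The denominator degrees of freedom will be based on the method proposed by Kenward-Roger". On non-convergence it says: "If the model fails to converge due to the UN covariance assumption, a compound symmetry (CS) covariance structure will be used". On missing data: "assuming that the data are missing at random, no imputation of missing data will be performed".

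Protocol section 12.3.4.2 has the same rule: "If there is a convergence problem due to the use of an unstructured covariance matrix, a compound symmetry covariance structure will be used".

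The rule reaches further than this one model. SAP section 9.6.2.1.2 makes the 108/110 analysis similar apart from the fixed effects. For relative change in ppFEV₁, BMI, weight, CFQ-R and the z-scores, SAP section 9.6.2.4 says "the analysis will be similar to the analysis of absolute change in ppFEV₁ from baseline".

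Two other provisions of SAP section 9.6.2 matter. The MMRM stops at the last visit where roughly 70% of the parent-study subjects remain, and no between-group hypothesis is tested. The output is an LS mean, standard error and 95% CI per visit and group, next to observed descriptive statistics.

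**The concern.** The plan moves from the least restrictive covariance to nearly the most restrictive in one step. Compound symmetry, as usually understood, has two parameters: one variance for every visit from Day 15 to Week 96, and one correlation for every pair of visits. The SAP does not write the word homogeneous, but nothing in it suggests the heterogeneous form.

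Two things can go wrong if that shape does not hold.

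- **Standard errors.** With one pooled variance, visits with larger true variance get intervals that are too narrow, and visits with smaller true variance get intervals that are too wide. Kenward-Roger allows for estimating the chosen covariance, not for choosing the wrong one. This needs no dropout.
- **LS means.** After dropout, the model implicitly predicts a subject's later values from the earlier ones through the fitted covariance. A wrong covariance gives wrong predictions. If dropout depends on observed outcome, the errors do not average out.

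The last modelled visits carry the plan's long-term efficacy information, and that is where both errors are largest.

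**Working it through.** The documents give no SD, correlation, dropout rate or precision for these models, so there is no stated figure to reproduce. The check has four parts.

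**1. How large is the unstructured matrix?** With k visits it has k(k+1)/2 parameters. SAP Table 11-2 gives ten visits for spirometry and CFQ-R: 10 × 11 / 2 = 55. Weight, height and BMI start at Week 8, giving nine visits: 9 × 10 / 2 = 45. SAP section 6.2 reports 464 subjects from Study 106 and 227 from Study 108, the latter over three groups. Failure is unlikely for ppFEV₁ in 464 subjects. It is more plausible in 108/110 and in the z-score subsets under 20 years.

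**2. Where does the 70% rule stop the model?** If the base is the number enrolled in Study 110, up to 30% are missing at the last modelled visit. If the base is the parent study, take the protocol synopsis counts as an assumed size:

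- Study 106: 0.70 × 490 = 343; (464 − 343) / 464 = 26% missing.
- Study 108: 0.70 × 300 = 210; (227 − 210) / 227 = 7% missing.

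The last modelled visit may therefore come before Week 96.

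**3. Interval width with complete data.** In a balanced design, compound symmetry gives each visit mean the variance s²/n, where s² is the average of the visit variances. Assume the SD rises linearly from 6 to 10 over ten visits. The SDs average 8 with variance (4/9)² × 99/12 = 1.63, so s² = 64 + 1.63 = 65.63 and s = 8.10.

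- Week 96: 8.10 / 10 = 0.81, so the interval is 19% too narrow. Coverage is 2Φ(1.96 × 0.81) − 1 = 89%.
- Day 15: 8.10 / 6 = 1.35, so the interval is 35% too wide.

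**4. Simulation with dropout.** One group of 232 (half of 464; the split is not stated), ten visits at the SAP weeks, true change 0, 600 replicates per scenario. Assumed SD is about 8 points, or between 6.5 and 10 where it varies. Dropout is random, or more likely after a low last value. Intervals are Wald with multiplier 1.97; the Kenward-Roger adjustment was not coded and would be small at this n. The Monte Carlo error of a 95% coverage is √(0.95 × 0.05 / 600) = 0.9 percentage points.

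Results under compound symmetry at the last visit. SE ratio is the reported SE divided by the actual SD of the estimate; below 1 means too narrow.

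| True shape | No dropout: SE ratio, coverage | 30% random: bias, coverage | 30% outcome-dependent: bias, SE ratio, coverage |
|---|---|---|---|
| Compound symmetry | 1.02, 95.0% | +0.03, 92.7% | +0.01, 1.00, 93.8% |
| Constant variance, partly decaying correlation | 0.99, 95.0% | −0.05, 93.5% | −0.17, 0.98, 93.3% |
| Constant variance, AR-type decay | 1.04, 96.2% | +0.01, 93.3% | −0.39, 0.92, 88.0% |
| Rising variance (random slopes) | 0.78, 86.3% | −0.01, 86.7% | +0.77, 0.76, 66.0% |
| Rising variance, partly decaying correlation | 0.83, 89.7% | +0.01, 88.2% | +0.32, 0.82, 86.3% |
| Shrinking variance | 1.27, 98.8% | +0.03, 98.3% | −0.70, 1.17, 83.5% |

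The unstructured fit had bias between −0.05 and +0.04 and coverage of 92.0% to 96.7% in every scenario run, including 50% dropout.

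The signs can be explained. When correlation decays, compound symmetry carries a low value too far forward, so predicted late values are too low. When variance rises, it carries too little forward, so predicted late values are too high. Shrinking variance does the reverse.

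A second simulation (n = 232, 26% outcome-dependent dropout, four assumed shapes that are not compound symmetry) compared possible fallbacks. Plain compound symmetry covered 76% to 91%. Heterogeneous Toeplitz covered 88% to 97% and heterogeneous compound symmetry 88% to 94%; each matched or beat plain compound symmetry in every shape. Heterogeneous AR(1) did worse than plain compound symmetry when variance rose: bias +0.76 to +1.03, coverage 66% to 76%.

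**The case against.** The strongest reply is that this is a contingency inside a secondary analysis. It matters only if the unstructured fit fails, and with 464 subjects that is unlikely for ppFEV₁. If the 70% rule stops the model early, the matrix shrinks further: stopping at Week 48 leaves six spirometry visits and 21 parameters. Bias in the means also needs outcome-related dropout. Several documented exits (commercial drug, another sponsor study, genotype-based sponsor decisions) need not select poor responders, and under random dropout the bias was about zero in every shape. There is no between-group testing, and the observed summaries by visit include the SD, so a changing variance would be visible. All of this stands and limits the severity. It does not remove the point: the interval error under changing variance needs no dropout, and a visible SD does not correct a reported CI.

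A reader might infer that the fallback would make late intervals too narrow and the Week 96 mean too favourable. The documents do not support that as a general statement. Both directions together need variance to rise with time, which no section quantifies. It is plausible for the Study 106 placebo group, whose efficacy baseline falls just before Study 110 dosing (SAP section 9.1), and for weight and BMI in growing adolescents. For the other modelled groups the baseline precedes parent-study dosing, so change at Day 15 may already be as variable as later.

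A reader might also infer that compound symmetry makes the missing-at-random assumption false. It does not. That assumption concerns why data are missing; what fails is the validity of the likelihood estimates under a wrong covariance model.

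**Conclusion.** The gap is real: there is a single step from unstructured to compound symmetry, model-based inference throughout, and the rule extends to all modelled continuous endpoints. If the fallback is used and its shape is wrong, intervals at the last visit kept by the 70% rule can be too narrow or too wide even with complete data (SE ratio 0.78 to 1.27 in the shapes tried). With 30% outcome-dependent dropout, LS means can also be biased in either direction (−0.70 to +0.77 points), with coverage of 66% to 93%. Only if variance rises with time are late intervals too narrow and, when low responders leave, late means too high.

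These sizes rest on assumed SDs, correlation shapes, dropout rates and an equal split of the Study 106 subjects. They show what can happen, not what will. Severity is minor to moderate, because the trigger is conditional and the estimates are secondary and untested.

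**What to change.** In SAP section 9.6.2.1.1, replace the single fallback with an ordered list, taking the first structure that converges:

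1. Heterogeneous Toeplitz (for ten visits, 10 variances + 9 correlations = 19 parameters).
2. Heterogeneous compound symmetry (10 + 1 = 11 parameters).
3. Homogeneous compound symmetry, only if neither converges, with empirical (sandwich) standard errors and a compatible degrees-of-freedom method in place of Kenward-Roger. This corrects the standard errors but not any dropout bias, and the SAP should say so.

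Leave heterogeneous AR(1) out. It can be more biased than plain compound symmetry here, and it treats the unequally spaced visits (gaps of 42, 56 and 84 days in SAP Table 11-2) as equally spaced. Toeplitz also counts visits by order, but each lag has its own correlation, so it is less restrictive.

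State that the list applies to 108/110 and to all other continuous endpoints, and report the structure used for each.

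The cost is a sentence or two in the SAP before data lock and a little more programming. Late-visit intervals may be wider, and Kenward-Roger degrees of freedom are lost in the last step.
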